### 5. Statistical Methodology

Three primary outcomes of interest, anemia, depression and treatment failure, will be analyzed using inferential statistics. Statistical evaluation will be performed with the most current release version of the software package SAS® [7]

#### 5.1 Analysis sets

There are no specific inclusion or exclusion criteria. However, women with a language barrier, a non-hormonal or not newly prescribed baseline medication or women who are pregnant at study enrollment will be excluded from the analysis. The final analyses will include both an "as treated" (AT) and an "intention-to-treat" (ITT) analysis. All women who are not excluded from the analysis will be assigned to the ITT and AT population at baseline. Only women with follow up information will be considered for longitudinal analysis (e.g. distribution of outcomes over time, incidence rates, regression). Women who never started their prescribed baseline medication will be considered in the ITT analysis, but excluded from the AT analysis. The safety conclusions of the study will be based on the AT analysis.

Supporting document SOP BMT 01.09 – Doc 5002.02 – Effective date 21.03.2017

This study follows three cohorts: users of Visanne (DNG), users of other medication approved for the treatment of endometriosis (OAED) and users of non-approved hormonal medications prescribed for endometriosis treatment or those approved only in some participating countries (NAED).

Distribution of women, population characteristics (baseline and follow up) as well as clinical outcomes will be presented for the following cohorts and sub-categories.

Cohort Sub-category for presentation	
DNG	Complete cohort
OAED	GnRH-a, Danazol, complete cohort
NAED	Combined hormonal contraceptives, other progestins, complete

The cohorts consist of new users (starter and restarter) or switcher of a hormonal endometriosis treatment. For the primary analysis, outcomes of interest or adverse events will be assigned to the treatment at the time the outcome or the event occurred. Women with multiple exposure or unspecific treatment will be specified as "Allocation unknown". Women who stopped their treatment will be assigned to an "Ex-use" cohort.

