1. INTRODUCTION

Endometriosis is a common, chronic, gynecological disease characterized by pain and impaired fertility. Prevalence estimates vary widely, however, the proportion of premenopausal women living with endometriosis is thought to be approximately 10% [1]. Endometriosis causes chronic inflammation, ovarian cyst formation, fibrosis and adhesions [1]. There seems to be little correlation between the extent of the disease and severity of pain experienced [2]. However, symptoms seem to respond to decreased circulating estrogen [3] and the mainstay of medical treatment is hormonal induced anovulation and a reduction in endogenous estrogen production.

While currently approved medications for endometriosis have proven to be effective in decreasing pelvic pain, many have clinically relevant side-effects. Danazol, a testosterone analogue, can cause androgenization and GnRH agonists are known to decrease bone mineral density. Consequently, treatment for endometriosis with these medications needs to be stopped after 6-12 months. Post-treatment endometrial lesions tend to regenerate, with many women's symptoms reoccurring 1-2 months after the cessation of treatment. Some countries in Europe also allow the use of progestogens for the treatment of endometriosis, however, there is currently no pharmaceutical preparation licensed for the treatment of endometriosis in all member states of the European Union.³

Dienogest (DNG) is a 19-nortestosterone derivative progestogen that is highly selective for progesterone receptors [4]. DNG has been available as part of a low-dose combined oral contraceptive containing 2mg of dienogest and 30µg of ethinylestradiol (DNG/EE) in Germany since 1995. As a progestin in DNG/EE, DNG is known for having strong endometrial effects that improve dysmenorrhoea and decrease the duration of menstrual bleeding [5]. In addition, progestogens may also modulate pain associated with endometriosis by dampening neuronal activity [3]. As a monotherapy for the treatment of endometriosis DNG 2mg/day has been available in Japan since 2008. In Japan it has been found to be a reliable and effective treatment for dysmenorrhea, premenstrual pain, dyspareunia and diffuse pelvic pain associated with endometriosis associated pelvic pain with improved tolerability compared with 3.75mg leuprolide acetate (LA) [7-8]. Unlike LA, DNG has minimal effects on bone density and may offer women a new option for the long-term control of endometriosis symptoms.

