2. STUDY OBJECTIVES

The primary objective of the study is to assess safety aspects of Dienogest 2 mg/day (Visanne[®]) used as endometriosis therapy and of other hormonal treatments for endometriosis in a study population that is representative for the actual users of the individual preparations. This includes an estimate of the absolute risk of rare serious adverse outcomes.

The main clinical outcomes of interest for the short and long-term follow-up are:

- Medical intervention for anemia induced by cyclical bleeding disturbances (anemia)⁴
- First time occurrence of clinically relevant depression, or worsening of existing depression
- To analyze discontinuation patterns of DNG and other endometriosis treatments due to treatment failure (e.g. re-occurrence of pain, adverse drug reaction)

Secondary objectives are:

- To characterize the baseline risk of users of the individual formulations (lifetime history of co-morbidity, risk markers, co-medication, sociodemographic and lifestyle data).
- To analyze the drug utilization pattern of DNG and other endometriosis treatments in a study population that is representative for typical use of the individual preparations under routine medical conditions.
- To investigate risks of short and long-term use of DNG and of established endometriosis treatments in adolescent women.

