#### 1.1 Rationale and background

Dienogest (DNG) is a 19-nortestosterone derivative progestogen that is highly selective for progesterone receptors [1]. As a progestin in DNG/EE, DNG is known for having strong endometrial effects that improve dysmenorrhea and decrease the duration of menstrual bleeding [2]. In addition, progestogens may also modulate pain associated with endometriosis by dampening neuronal activity [3]. It is not known what influence DNG will have on bleeding disturbances associated with endometriosis over a longer time frame or the potential influence of DNG on mood disturbance and depression in endometriosis patients.

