#### 5.3 Analysis of population characteristics

#### 5.3.1 Descriptive statistics

All background data such as patient characteristics, socio-economic characteristics, endometriosis pattern and gynecological history, family and medical history, concomitant medication as well as mood will be described by presenting frequency distributions and/or basic summary statistics (number of patients with an observation [n], mean, standard deviation [SD], median, 25th [Q1] and 75th [Q3] percentiles, minimum [Min] and maximum [Max]). Unless otherwise specified, the mean and median for a continuous variable will be listed to 1 more decimal place than the original (raw) values and the SD will be listed to 2 more decimal places than the original values. The minimum and maximum will be listed to the same number of decimal places as the original values.

Categorical variables will be summarized using frequencies and percentages. Each table will list both absolute and relative numbers (%), providing the total amount of available data for each variable. Total number of women (100%) for the presented (sub-) population is given in the first line of each table. Additional categories may be derived from data and are denoted by <<CATEGORY>> in the table templates. Percentages will be listed to 2 decimal places. In cases where the percentage calculated is > 0% and < 0.01%, three decimal places will be listed with the absolute value.

In addition, age-standardized proportions are presented for selected baseline characteristics, history of co-morbidity, risk markers and co-medication. Therefore, the most represented cohort will used as the referenced standard population.

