#### 6.2.2 Definition of subgroups

Variable label	Definition
Country	Germany vs. Poland vs. Hungary vs. Switzerland vs. Russia vs. Ukraine
Long-term user	15 months or more of continuous EMT intake
EMT user type	Starter vs. restarter vs. switcher
Diagnosis classification	Diagnosis of endometriosis confirmed via surgery / laparoscopy vs. diagnosis based on clinical symptoms
Age categories	< 20 vs. 20 to < 30 vs. 30 to < 40 vs. >= 40
Age-standardization	Referenced population: NAED cohort

12 ICD10-Codes Version 2009

13 ATC-Codes Version 2010

14 OPS-Codes Version 2009

Supporting document SOP BMT 01.09 – Doc 5002.02 – Effective date 21.03.2017

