### Section D Comparisons and Inferential Statistics of Primary Outcomes

#### Section D-1 New anemia and reoccurrence of anemia

Table D-1.1.1 Incidence rate ratio of new anemia and reoccurrence of anemia between EMT user cohorts, AT population

Comparison	Cohort	No. of	WY	Incidence	Incidence Rate Ratio
Group		events		rate*	(95% CI)
	DNG	xx	xxxxx	x.xxxx	x.xxxx
1	OAED	xx	xxxxx	x.xxxx	(x.xxxx - x.xxxx)
2	DNG NAED	xx xx	xxxxx	x.xxxx x.xxxx	x.xxxx (x.xxxx - x.xxxx)
2	DNG	xx	xxxxx	x.xxxx	x.xxxx
3	Ex-use	XX	xxxxx	x.xxxx	(x.xxxx - x.xxxx)

Note: \*Incidence rate per 10^4 women years

Supporting document SOP BMT 01.09 – Doc 5002.02 – Effective date 21.03.2017

Table D-1.1.2 Risk of new anemia and reoccurrence of anemia obtained from Cox model (HR), AT population

Cohort	No. of	No. of WYs		Hazard Ratio (95% CI)		
	events			Crude HR	Adjusted HR	
DNG	xx	xxxxx	x.xxxx	x.xxxx	x.xxxx	
OAED	XX	xxxxx	x.xxxx	(x.xxxx - x.xxxx)	(x.xxxx - x.xxxx)	
DNG	xx	xxxxx	x xxxx	x xxxx	X.XXXX	
NAED	xx	xxxxx	x.xxxx	(x.xxxx - x.xxxx)	(x.xxxx - x.xxxx)	
DNG	VV		V VVVV	V VVVV	V	
Ex-use	xx xx	XXXXX	x.xxxx x.xxxx	x.xxxx (x.xxxx - x.xxxx)	x.xxxx (x.xxxx - x.xxxx)	
	DNG OAED  DNG NAED	DNG XX DNG XX DNG XX DNG XX NAED XX	DNG XX XXXXX  DNG XX XXXXX  DNG XX XXXXX  DNG XX XXXXX  DNG XX XXXXX	DNG XX XXXXX X.XXXX OAED XX XXXXX X.XXXX  DNG XX XXXXX X.XXXX  NAED XX XXXXX X.XXXX  DNG XX XXXXX X.XXXX	DNG     XX     XXXXXX     XXXXXX     XXXXXX       OAED     XX     XXXXXX     XXXXXX     XXXXXX       DNG     XX     XXXXXX     XXXXXX     XXXXXX       NAED     XX     XXXXXX     XXXXXX     XXXXXX       DNG     XX     XXXXXX     XXXXXX     XXXXXX	

Note: \*Adjusted for age, history of bleeding and history of anemia.

Section D-2	New depression or deterioration of existing depression
	Incidence rate ratio of new depression or deterioration of existing depression between EMT user cohorts, AT population Risk of new depression or deterioration of existing depression obtained from the Cox model (HR), AT population
Section D-3	Treatment failure
Section D-3.1	Incidence rate ratio of treatment failure between EMT user cohorts, AT population
Section D-3.2	Risk of treatment failure obtained from the Cox model (HR), AT population

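### The supplementary DNG vs NAED comparison may not contrast dienogest with dienogest-free treatment, because NAED includes combined contraceptives that contain 2 mg dienogest and the SAP does not separate them

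*SAP*

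**What the plan says.** The objective in Protocol section 2 is "to assess safety aspects of Dienogest 2 mg/day", that is Visanne, together with other hormonal treatments. SAP 5.1 defines the DNG cohort as Visanne users. OAED is GnRH agonists and danazol. NAED is presented as "Combined hormonal contraceptives, other progestins, complete" cohort. The flow chart in SAP 3.2 also lists combined contraceptives first under NAED, again without exception.

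Protocol section 1 states that "DNG has been available as part of a low-dose combined oral contraceptive containing 2mg of dienogest" and 30 µg of ethinylestradiol, in Germany since 1995. SAP 3.1 names Germany as the country where the study began. Protocol section 4 (footnote on the non-interference approach) opens enrolment to new users whatever their estrogen or progestin.

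SAP 1.1 mentions the combined product in its rationale: "As a progestin in DNG/EE, DNG is known for having strong endometrial effects". It then says that the influence of DNG on bleeding disturbances over the longer term, and on mood and depression, is unknown.

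Section D plans three pairwise comparisons: DNG against OAED, NAED and ex-use. The anemia shells show an incidence rate ratio and then, in Table D-1.1.2, "Risk of new anemia and reoccurrence of anemia obtained from Cox model (HR), AT population". Depression and treatment failure follow the same pattern. Neither the shells nor the covariate lists in SAP 5.4.2 and Appendix III distinguish contraceptives by dienogest content.

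**The concern.** The background asks about dienogest, but the cohorts are defined by product and approval status. For most NAED treatments the two agree. For DNG/EE they do not: it contains the same 2 mg of the progestogen under study, yet it sits in the comparator. Because SAP 5.1 assigns an event to the treatment in use when it occurs, a woman who moves from Visanne to DNG/EE also moves from the DNG side of comparison 2 to the NAED side.

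Readers of a DNG vs NAED ratio for anemia or depression are likely to take it as evidence on dienogest against other hormonal treatment. If a material part of NAED is DNG/EE, that reading is not secure, and the planned outputs give no way to tell whether the part is material. In a safety study, an unexplained ratio near 1 or away from 1 in a supplementary comparison can be over-read either way.

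**Working it through.** **1. The plan's own figure and whether it is touched.** No sample size is stated for DNG vs NAED. The only sample size for the safety outcomes is 8,400 women-years on DNG, 4,200 on reference and 84,000 in total (Protocol section 12 and SAP section 4, Tables 2 and 3). Inputs: one-sided α 0.0083, power 90%, hazard ratio to exclude 2 with true ratio 1, event rate 0.01 per woman-year, DNG to reference 2:1, DNG share 10%.

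- Events = (z₀.₉₉₁₇ + z₀.₉₀)² / [(2/3)(1/3)(ln 2)²] = 126.6.
- Women-years = 126.6 / 0.01 ≈ 12,660, split 2:1 into about 8,442 and 4,221.
- Total = 8,442 / 0.10 ≈ 84,400.

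This reproduces the stated figures. The hypotheses in SAP 5.2 define each ratio as DNG vs OAED, and OAED contains no contraceptives, so neither the tests nor these numbers depend on how DNG/EE is classed.

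**2. Effect on comparison 2.** Let R be the true rate ratio of Visanne to dienogest-free NAED. Let f be the DNG/EE share of NAED women-years and k the DNG/EE event rate relative to dienogest-free NAED. With constant rates, the NAED rate is the mixture 1 − f + f·k, so

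observed ratio = R / (1 − f + f·k).

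The documents give neither f nor k, so both are assumptions. If DNG/EE has exactly the Visanne rate, then k = R. If it has half the rate of other NAED treatments, then k = 0.5.

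| f | R = 2.0, k = R | R = 1.5, k = R | R = 2.0, k = 0.5 |
|---|---|---|---|
| 0% | 2.00 | 1.50 | 2.00 |
| 5% | 1.90 | 1.46 | 2.05 |
| 10% | 1.82 | 1.43 | 2.11 |
| 20% | 1.67 | 1.36 | 2.22 |
| 40% | 1.43 | 1.25 | 2.50 |

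For example, at f = 20% and R = 2.0: 2/(0.8 + 0.2 × 2) = 2/1.2 = 1.67 with k = R, and 2/(0.8 + 0.2 × 0.5) = 2/0.9 = 2.22 with k = 0.5.

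**3. What the documents say about k.** Protocol section 1 credits DNG/EE with improving dysmenorrhoea and shortening menstrual bleeding. It also describes bleeding disturbance as a class effect of progestogens, with 72% of women in a 52-week study of dienogest alone reporting intermenstrual spotting or bleeding. For mood, it cites a review finding no increased depression risk in oral contraceptive users compared with non-users. These statements do not fix k, but they give no basis for assuming k = R.

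**4. Whether the split is feasible.** The baseline questionnaire (SAP Appendix I, question 1) records the name of the prescribed medication. The follow-up questionnaire (Appendix II, question 1) records brand name with start and stop dates.

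**The case against.** The strongest reply is that NAED is a supplementary cohort with no margin or test attached, and that the study compares products and regimens as prescribed. DNG/EE adds ethinylestradiol and is a different treatment, so classing it with other contraceptives is defensible. Daily exposure need not match either: Visanne is given as 2 mg per day, while the baseline form has to ask whether a contraceptive is taken in an extended regimen. The C-1 shells already show combined contraceptives and other progestins in separate columns, so DNG can be read against progestins alone. Section D also offers OAED and ex-use as comparators, neither of which involves current contraceptive use. Finally, no text shows that any NAED woman uses DNG/EE, and its availability is documented for Germany only, one of six countries.

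All of this stands, and it limits the point to a clarification. It does not close the gap, because none of the planned outputs reports how much of NAED is DNG/EE.

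A reader might infer that comparison 2 sets dienogest partly against itself, or that it hides harm. The documents support neither. Only the progestogen component is shared, and the direction of any distortion depends on k, which is unknown.

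A reader might also infer that this is the most precise ratio in the report, because SAP 5.3.1 says "the most represented cohort will used as the referenced standard population" and SAP 6.2.2 gives "Referenced population: NAED cohort". Those lines concern age standardization of baseline characteristics. They suggest that NAED is the largest cohort but do not establish its events or women-years, and ex-use time could rival it, since SAP section 4 expects most women to stop or change treatment.

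**Conclusion.** The point holds as a modest one. The SAP places dienogest-containing combined contraceptives in NAED without saying so and without separating them, so the DNG vs NAED ratios for anemia and depression may not contrast dienogest with dienogest-free treatment. The formal DNG vs OAED hypotheses and their sample size are unaffected.

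The size ranges from nothing at f = 0 to a true 2.0 appearing as 1.43 at f = 40%, if DNG/EE has the Visanne rate. With a DNG/EE rate below that of other NAED treatments, the same misclassification moves the ratio away from 1, to 2.50 at f = 40% when that rate is half. These figures illustrate assumed values of f and k and do not estimate a bias in this study.

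Treatment failure is left aside: whether women stay on a given product is naturally a product-level question, and the shared component matters less there.

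**What to change.** In SAP 5.1, state that dienogest-containing combined contraceptives belong to NAED and flag them from the product names recorded at baseline and follow-up. Report their women-years and events within NAED as one added column in the complete-cohort anemia and depression incidence tables (C-1.1.1, C-1.1.2, C-1.2.1 and C-1.2.2). In D-1 and D-2, add a sensitivity run of comparison 2 with these women-years excluded from NAED, shown beside the full NAED result. Leave the DNG vs OAED analyses and the stratified tables as planned.

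The cost is one coding flag and a little extra programming, with slightly fewer NAED women-years in the added run. If the share proves small, the added column shows it and the question is closed.

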### 5.2 Hypothesis

Based on available data and pharmacological/pharmacokinetic considerations the a priori assumption is that use of DNG is not associated with an increased risk of anemia compared to approved hormonal medications used in the treatment of endometriosis ("endometriosis medications"). It is probable that statistical comparisons of DNG vs. other endometriosis medications will not show a difference. Therefore, a non-inferiority design to investigate the anemia risk of DNG had been chosen. The analysis will be based on the comparison of the upper confidence limit for the point estimate of the anemia hazard ratio with the predefined non-inferiority margin (cf. section 4).

 $H_0$  and  $H_A$  denote the null and alternative hypotheses, respectively.  $HR_{Anemia}$  is defined as the hazard ratio for anemia for DNG vs. OAED.

$$H_0: HR_{Anemia} \geq 2$$

$$H_A$$
:  $HR_{Anemia} < 2$ 

For clinically relevant depression (first episode or worsening), the a priori assumption is that no approved treatment for endometriosis is associated with a higher risk of depression compared with untreated endometriosis. A non-inferiority design has been chosen, with primary analysis based on the comparison of the upper confidence limit for the point estimate of the depression hazard ratio with the predefined non-inferiority limit (cf. section 4).  $HR_{Depression}$  is defined as the hazard ratio for depression (newly diagnosed or worsening) for DNG vs. OAED

$$H_0: HR_{Depression} \geq 2$$

$$H_A: HR_{Depression} < 2$$

Supporting document SOP BMT 01.09 – Doc 5002.02 – Effective date 21.03.2017

There are both pharmacological and clinical indications that suggest that DNG may be superior to other endometriosis medications as a long-term treatment for endometriosis. That is, a statistical comparison of DNG vs. other endometriosis medications may show a difference in 'treatment failure', with DNG users continuing on treatment for longer periods of time. 'Treatment failure' is defined as cessation of treatment caused by lack of efficacy, loss of efficacy or an adverse drug reaction and does not include women who stop treatment after pre-defined treatment periods (e.g. after six months for GnRH agonists). In addition, combined treatment with GnRH, an estrogen and/or a progestogen (add-back therapy) will be considered as a single treatment regimen. In cases where add-back therapy is used the predefined end-point is the cessation of the add-back therapy. A superiority design to investigate 'treatment failure' for DNG has been chosen. The analysis will be based on a 5%-point difference (difference of 0.05) of DNG vs. other endometriosis medications.  $OR_{TreatmentFailure}$  is defined as the odds ratio for 'treatment failure' for DNG vs. OAED.

 $H_0: OR_{TreatmentFailure} \ge 1$ 

 $H_A: OR_{Treatmentfailure} < 1$ 

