#### 5.3.2 Stratifying factors

The numbers of patients enrolled and included in the analysis populations will be tabulated by defined stratifying variables for the AT and ITT population, if appropriate.

Baseline and follow-up population characteristics will be presented for the AT and ITT population and stratified by

Supporting document SOP BMT 01.09 – Doc 5002.02 – Effective date 21.03.2017

- (1) Country
- (2) EMT user type: starter vs. switcher vs. restarter
- (3) Diagnostic classification: Diagnosis confirmed by surgery vs. diagnosis based on clinical symptoms,

if not otherwise specified.

The analysis of the primary and secondary outcomes will be presented for the AT population, anemia and depression additionally for the ITT population. Primary and secondary outcomes are stratified by subgroups if appropriate:

- (1) Country
- (2) EMT user type: starter vs. switcher vs. restarter
- (3) Diagnostic classification: Diagnosis confirmed by surgery vs. diagnosis based on clinical symptoms

Selected outcomes regarding the baseline risk (lifetime history of co-morbidity, risk markers, co-medication, socio-demographic and lifestyle data), will be additionally displayed by subgroups as follows:

- (1) Age categories: < 20 vs. 20 to < 30 vs. 30 to < 40 vs. >= 40
- (2) Age standardized

Additional subgroups will be added for selected outcomes if appropriate.

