#### 5.4.2.1 Cox Proportional Hazard Model

Time-to-event (survival) analyses will be undertaken using Cox proportional hazard models (Cox model) to describe how the hazard increases for each unit increase of the regressor variables. Crude and adjusted hazard ratios (HR) comparing subpopulations under study will be calculated for all primary outcomes and 95% HR confidence limits (Wald) are provided. The crude model refers to a univariable model which includes exposure as the only explanatory factor. Potential predefined event-specific prognostic factors (section 5.4.2) are included in multiple models. In the Cox model, recurrent events are included.

18

 See Appendix III for all potential prognostic factors for each primary and secondary outcome.

Supporting document SOP BMT 01.09 – Doc 5002.02 – Effective date 21.03.2017

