#### Section C - Clinical Outcome

Section C provides incidence rates of primary (Section C1), secondary (Section C2) and safety outcomes (Section C3) and other outcomes of interest (Section C4).

Section C-1 Primary outcomes

The analysis of the primary outcomes (Section C1) is stratified by country, EMT user type and diagnosis classification.

Anemia

Incidence rate of Anemia

Depression

Incidence rate of Depression

Treatment failure

Incidence proportion of treatment failure

Section C-2 Secondary Outcomes

The analysis of the secondary outcomes (Section C2) is stratified by country, EMT user type and diagnosis classification.

Supporting document SOP BMT 01.09 – Doc 5002.02 – Effective date 21.03.2017

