#### Section D-3 Treatment Failure

- Incidence Rate Ratio of Treatment Failure between EMT user cohorts (IRR)
- Risk of Treatment Failure measured as HR (Cox model)
   Crude and adjusted HR

Supporting document SOP BMT 01.09 – Doc 5002.02 – Effective date 21.03.2017

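### The primary treatment-failure hypothesis is set on an odds ratio, but only a rate ratio and Cox hazard ratios are planned, and none is named as the deciding test

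*SAP*

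**What the plan says.** SAP 5.2 gives treatment failure a superiority hypothesis. The parameter "is defined as the odds ratio for 'treatment failure' for DNG vs. OAED"; the null is OR ≥ 1 and the alternative OR < 1. Just before that, the section states: "The analysis will be based on a 5%-point difference (difference of 0.05) of DNG vs. other endometriosis medications". Protocol 11 carries the same sentence about the difference, has no odds ratio, and plans Cox regression for the final analyses.

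The analysis sections use other measures. SAP 5.4.2.1 says: "Crude and adjusted hazard ratios (HR) comparing subpopulations under study will be calculated for all primary outcomes", and adds that "95% HR confidence limits (Wald) are provided". SAP 8, Section D-3, lists an incidence rate ratio and a crude and adjusted Cox HR. The mock tables repeat this, with D-3.2 titled "Risk of treatment failure obtained from the Cox model (HR), AT population". SAP 8, Section C-1, has "Incidence proportion of treatment failure", which mock Table C-1.3.1 shows cohort by cohort per 100 treatment starts, without a contrast.

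On the population, SAP 5.3.2 says: "The analysis of the primary and secondary outcomes will be presented for the AT population, anemia and depression additionally for the ITT population". Treatment failure is therefore presented as-treated only.

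SAP 4 places three hypotheses under Bonferroni-Holm, but describes testing each at one third of the usual level, 0.0167. Table 4 labels 0.0167 one-sided. Tables 2 and 3 treat it as two-sided, that is 0.0083 one-sided.

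**The concern.** A multiplicity procedure needs one p-value per hypothesis. For anemia and depression, SAP 5.2 names the hazard ratio and its upper confidence limit, and that ratio is then planned. For treatment failure it names a quantity that no model or table produces. Three scheduled results (IRR, crude HR, adjusted HR) could stand in for it, and none is designated. The choice could be made after the results are seen, and none of the three tests the hypothesis on its stated scale.

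Taking 5.2 literally would be worse than replacing it. The only failure proportion in the plan uses treatment starts as its denominator. SAP 5.2 itself notes that GnRH-agonist courses may end by plan at about six months. If time on treatment differs between cohorts, an odds ratio per start mixes failure risk with course length.

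**Working it through.** **1. Hypothesis against planned output.**

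| Measure | In SAP 5.2 | Planned between-cohort result |
|---|---|---|
| Odds ratio | yes (H0: OR ≥ 1) | none |
| Difference of 0.05 | yes | none |
| Incidence rate ratio | no | SAP 8 and mock D-3 |
| Cox HR, crude and adjusted | no | SAP 5.4.2.1, SAP 8 and mock D-3 |

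Outside 5.2, the odds ratio appears only in the abbreviation list.

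**2. Reproducing Table 4.** Inputs: 0.30 vs 0.25, one-sided 0.0167 (z = 2.127), power 90% (z = 1.282), allocation 2:1. Stated size: 1,475 reference and 2,950 DNG women-years (WY). (2.127 + 1.282)² = 11.62.

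- Two proportions, unpooled: 11.62 × (0.30×0.70 + 0.25×0.75/2) / 0.05² = 1,412 in the reference cohort.
- Two proportions, reference variance in both cohorts: 11.62 × 1.5 × 0.21 / 0.05² = 1,464.
- Hazard ratio 0.25/0.30 = 0.833: events = 11.62 / [(2/9) × (ln 0.833)²] ≈ 1,574. The mean rate is (2×0.25 + 0.30)/3 = 0.267 per WY, so 5,902 WY in all and about 1,968 in the reference cohort.

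The stated 1,475 is within 1% of 1,464 and well below 1,968. Table 4 is close to a two-proportion calculation. So the outcome is sized near one scale, hypothesised on another and analysed on a third.

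**3. Power of the planned Cox HR.** Power = Φ(√(events × 2/9) × |ln HR| − 2.127).

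- Table 4 size, 0.25/0.30 as rates: events = 2,950×0.25 + 1,475×0.30 = 1,180; Φ(16.19 × 0.1823 − 2.127) = 79.5%. For 90%: 1,574 / (0.10×0.25 + 0.05×0.30) = 1,574/0.04, or about 39,300 total WY.
- Table 4 size, 0.25/0.30 as one-year proportions: HR = ln 0.75 / ln 0.70 = 0.807. Power is 91% with 1,180 events (each woman counted as one WY). It is 95% with 1,375 events (WY as time at risk).
- Target of 84,000 WY at 10%/5% shares, as rates: events = 8,400×0.25 + 4,200×0.30 = 3,360; Φ(27.32 × 0.1823 − 2.127) = 99.8%.

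**4. Scale.** Assume constant rates of 0.25 (DNG) and 0.30 (OAED) per WY, so HR = 0.833 throughout. The proportion failing per start is 1 − exp(−rate × duration); the durations are also assumed.

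- One year on each: 0.221 vs 0.259, OR = 0.81.
- One year on DNG, half a year on OAED: 0.221 vs 0.139, OR = 1.76.

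**5. Threshold.** The HR needed for success is exp(−z/√(events × 2/9)).

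| One-sided alpha | 1,180 events | 3,360 events |
|---|---|---|
| 0.025 (95% Wald limit) | 0.886 | 0.931 |
| 0.0167 (Table 4) | 0.877 | 0.925 |
| 0.0083 (reading in Tables 2–3) | 0.863 | 0.916 |

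The unstated rule decides any estimate lying between these values. The band narrows at the target size. All these thresholds assume independent events.

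**The case against.** The intended test is fairly clear: Protocol 11, SAP 5.4.2.1 and Section D-3 all point to Cox models, and a careful analyst would use one. That stands, and it makes the repair light. It does not settle crude against adjusted, and it leaves a primary null on a scale nobody will estimate. Because both documents also base the analysis on the difference, a risk difference with a defined time window would be another defensible repair. The HR is preferable because it is already scheduled and accounts for differing time on treatment.

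Crude against adjusted, and 95% limits against 0.0167, affect anemia and depression too. This is true; only the mismatch of parameter is specific to treatment failure.

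A reader might infer that the adjustment set can be picked after the final results. Protocol 11 has the Safety Monitoring and Advisory Council (SMAC) decide confounders before the first interim analysis, which limits that. The lists still disagree. The SAP 5.4.2 table gives age, depression history and pain severity. The text of 5.4.2 also includes user type and current or worsening depression as time-dependent, as does Appendix III. Protocol 11 names chronic pelvic pain, age and previous surgery.

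A reader might infer that the HR is the sizing scale because Table 4 cites the same reference as Tables 2 and 3. Table 2 does reproduce on the log-HR scale: at alpha 0.05/6, about 126.5 events, or 8,435 + 4,218 WY against 8,400 + 4,200 stated. Table 4 does not.

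A reader might also infer that the 95% limit spends 0.025/0.0167 = 1.5 times the allowed alpha. That holds only at the first Holm step on the one-sided reading; the second step is 0.025 itself.

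**Conclusion.** The concern holds as a defect of pre-specification and scale. A primary hypothesis that carries alpha is stated as OR ≥ 1 with a 5-point difference. The planned comparisons are an IRR and two versions of a Cox HR, and no one result is designated. The measures can differ in direction: OR 0.81 or 1.76 with HR fixed at 0.833. That illustration rests on assumed constant rates and course lengths. It shows that the OR is a poor parameter here and is no forecast of the result; the planned HR is unaffected.

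The 79.5% figure might suggest that the outcome is underpowered. The documents do not support that. The figure applies only at Table 4's own size and only if 0.25 and 0.30 are rates; even then, the roughly 39,300 WY needed is under half the 84,000 WY target, where power is 99.8%. That last figure assumes the 10%/5% shares. SAP 3.1, footnote 8, reports a comparator share well below plan and a recommended re-start for 2,000 OAED patients; it does not give the share finally reached.

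**What to change.** - **Hypothesis (SAP 5.2):** replace the OR with H0: HR for treatment failure ≥ 1 against HR < 1, DNG vs OAED. Describe 0.05 as the Table 4 planning effect, not the basis of the analysis.
- **Deciding estimate:** name the adjusted Cox HR in the AT population (D-3.2). Keep the crude HR, IRR and incidence proportions as supportive.
- **Covariates:** use the set confirmed by the SMAC, after reconciling the SAP 5.4.2 table, its time-dependent list, Appendix III and Protocol 11, including previous surgery.
- **Error rate:** report the p-value or confidence limit at the alpha of the multiplicity procedure, not the 95% Wald limit alone. Say whether that procedure is Holm or the fixed one-third split described in SAP 4, and whether 0.0167 is one- or two-sided.
- **Model details:** state the time origin and the censoring of stops that are not failures, consistent with SAP 5.2 and 5.4.4. SAP 5.4.2.1 includes recurrent events and Table C-1.3.1 counts repeat treatment starts. If these enter the model, use a robust variance clustered by woman.
- **Table 4:** label 0.30 and 0.25 as one-year proportions or as rates per WY.
- **Record:** document the change against Protocol 11.

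The cost is SAP wording, one table label and a documented change to the protocol's analysis section. The Cox model is already scheduled, and the follow-up questionnaire already collects start dates, stop dates and reasons for stopping.
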